### **3.2. Rationale for Treatment Duration Extension up to 48 Months**

The initial statistical analysis plan used detailed event rate projections based on an extensive review of the published literature (Refer to Appendix E) and determined that a sample size of 150 randomized subjects would be required for the primary endpoint analysis. Because of logistical reasons, subject accrual was completed in April 2016 with 171 patients randomized.

In February 2016, a blinded data review was done to project a more realistic estimate of FAP-related event rates at the completion of the trial with a maximum of 24 months of treatment. Based on this analysis, it was considered unlikely we would reach the projected 90 events before the end of the study. To reduce the risk of a false-negative trial (because of inadequate events after two years of study treatment in 171 randomized subjects), several mitigation options were explored. The protocol was amended to extend treatment duration to a maximum of 36 months. Over 90% of subjects who reached 24 months without an FAP-related event consented to the trial extension.

As of June 2017, there have been 53 FAP-related primary endpoint events. Under the current event rates and with an estimated trial end-date of April 2018, projections once again do not indicate a high likelihood of 90 events. Various statistical analyses, using Weibull methodology, indicate that under current hazard rate assumptions to maintain power  $\geq 85\%$ , an additional trial extension may be required. This protocol amendment offers all active subjects a longer-term blinded treatment until study completion at or before April 2019. This means, based on the date of randomization, a treatment extension of up to 36, 42 or 48 months. The study will complete for reasons defined in Section 4.2.

There have been five safety data monitoring committee meetings for CPP FAP-310 study, the most recent June 2017. To date, the DMC has not identified any safety issues and there have been no recommended protocol modifications due to safety. Additionally, for CPP FAP-310, the Medical Monitor performs a monthly blinded review of all adverse events to evaluate for events not commonly associated with drug exposure or to look for an increase in events above what is typical for the population under study.

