#### **4.4. Primary Outcome**

The primary objective of this trial is to determine whether the combination of CPP-1X plus sulindac is superior to either treatment individually, in delaying the time from the date of randomization to the date of the first occurrence of any FAP-related event in the subject as a whole. This includes: 1) FAP related excisional intervention involving the colon, rectum, pouch, duodenum and/or 2) clinically important events which includes progression to more advanced duodenal polyposis (Stage 2, 3 or 4), cancer or death. Section 8.2.14 provides complete detail.

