#### **9.2. Follow-up Endoscopies**

At six month intervals (+/- two weeks) – per Section 8.1, subjects will undergo repeat upper and lower endoscopy. At any interval assessment, if any subject requires an excisional intervention (as defined in Section 8.2.14), or has duodenal Spigelman stage progression (Stage 2, 3 or 4), the subject will be considered to have an FAP-related event and will come off study treatment.

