### **5.5.3 Analytic Methods for Time-to-Event Data**

The analytic method for the primary analysis will be a time-to-event analysis using the stratified log-rank test, as previously described. The stratified Cox proportional hazards regression models will be used for secondary assessments[7]. Graphical analyses (log-minus-log plots) will be used to check the assumption of constant hazard ratios. See Section 7.3 below for further details of the calculation of the stratified log-rank statistic.

For the primary analysis, two stratified log-rank tests will be performed with treatment coded as a binary value (i.e., 0 or 1). Time to event curves will be displayed using the method of Kaplan and Meier[8]. Additional analyses involving the overall 3-treatment group comparison, and use of additional study populations (see Section 4.) for the two pairwise treatment comparisons, will be performed as supplemental analyses.

If an FAP-related event occurs, that patient will be said to have an observed or uncensored event and will be considered a treatment failure. If a subject withdraws, that subject will be treated as a censored observation as of the last recorded clinic visit (endoscopic disease assessment).

If a subject has not progressed or is not known to have died at the date of analysis cut-off, time to first FAP-related event will be censored at the date of the last adequate endoscopy procedures before the cut-off date. Similarly, if a subject discontinues study participation due to toxicity and begins receiving other therapy, the time to FAP event will be censored at the date of the last adequate endoscopy procedure.

If a subject has two or more missing assessments, time to first FAP-related event for the subject will be censored at the time of last adequate evaluation prior to the missing assessment.

If a subject has no baseline assessment, time to first FAP-related event for the subject will be censored at the date of randomization.

See Section 5.5.6 below for further details of handling missing data. Every effort will be made to minimize the occurrence of censoring and missing data.

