### **5.5.6 General Procedures for Handling Missing Data**

Every reasonable effort will be made to continue follow-up of all study participants, including those who discontinue randomized therapy, to prevent data loss. It is recognized that missing values represent a potential source of bias in a clinical trial and so every effort will be undertaken to fulfill all the requirements of the protocol concerning the collection and management of data.

For the primary time to event analysis, the only possible patient outcome is an observed FAP-related event or a censored observation. Participants who are lost to follow-up will be censored at the time their status is last known, based upon data collected at the last recorded clinic visit. For patients who may have missed a study visit, every effort will be made to obtain endoscopic results at their close-out visit and those endoscopy results will be used for the primary analysis.

Secondary analysis data include the presence of a specific genetic mutation, and urinary metabolite concentrations (see Section 3.2.3). The main analysis of the secondary objectives will include collected data only, without imputing or weighting data to compensate for missing data. For sensitivity analyses involving secondary endpoints with missing data, we will use the last observation carried forward (LOCF) method to complete the missing data. Any sensitivity analysis that incorporates LOCF will be clearly noted. Sensitivity analyses of these data will be performed to explore study results more fully, in a manner consistent with ICH Guidance “*E9 Statistical Principles for Clinical Trials (February, 1998)*”.

All available efficacy and safety data will be included in data listings and tabulations. Data that are potentially spurious or erroneous or appear as outliers will be examined using standard data management operating procedures, prior to database lock and statistical analysis. These procedures will be fully described in the study report.

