### 7.3 Details of Calculating the Stratified Log-rank Z-Score

Patient follow-up will be analyzed in continuous time, although it is recognized that FAP event detection will cluster around scheduled study visits, at months 6, 12, 18, 24, 30, 36, 42 and 48 and event times may be tied as follow-up time is measured only to the nearest day. Censorings are possible at the baseline visit (month 0) for patients who dropped out of the trial before their first follow-up visit. The primary test statistic will be the stratified log-rank statistic. Each two-arm comparison will be performed separately. This will be implemented in SAS by specifying the TIES=DISCRETE option in PROC PHREG. The single agent treatments, respectively, will be coded as 1 and the combination treatment will be coded as 0. The square root of the score test chi-squared statistic will be calculated and the *sign* of the estimated log hazard ratio (+ if the HR>1 and – if the HR<1) will be attached. This results in the stratified log-rank Z-score. In symbols,  $Z_k = \text{sign}(\hat{\beta}) \times \sqrt{X^2}$ , where  $\hat{\beta}$  denotes the estimated log hazard ratio coefficient for treatment *A* in the Cox model and where  $X^2$  denotes the SCORE TEST chi-squared statistic reported within the “Testing Global Null Hypothesis: BETA=0” table at the top of the PHREG results section.

The following sample PHREG procedure could be used in SAS to derive the stratified log-rank Z-score:

```
proc phreg data=TwoArmData;
  model time*censor(1) = Treatment / rl ties=discrete;
```

```

strata Stratification_Factor;
title "Stratified Cox Regression Analysis for Single Agent vs Combination";
run;
quit;

```

NB: The model includes the variables time, censor, and treatment, only.

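### The two-missed-assessments censoring rule in SAP 5.5.3 is not limited to consecutive misses just before the event, so read literally it discards some documented primary events; the effect is small and the wording is easy to fix

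*SAP*

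**What the plan says.** SAP 5.5.3 gives a general rule for events: if one occurs, "that patient will be said to have an observed or uncensored event and will be considered a treatment failure". Censoring rules follow for withdrawal, analysis cut-off, and toxicity with other therapy. Then comes the rule at issue: "If a subject has two or more missing assessments, time to first FAP-related event for the subject will be censored". The section places the censoring date "at the time of last adequate evaluation prior to the missing assessment". A last rule censors subjects without a baseline assessment at randomization. The section refers to SAP 5.5.6 for further details of missing data but sets no order between the two.

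SAP 5.5.6 and Protocol 12.7 say that, for patients who may have missed a visit, endoscopy will be sought at close-out and "those endoscopy results will be used for the primary analysis". Protocol 12.1 has the event rule and the withdrawal, cut-off and toxicity rules, but not the missing-assessment rule.

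Three other places matter:
- Protocol 4.4 includes in the endpoint "progression to more advanced duodenal polyposis (Stage 2, 3 or 4), cancer or death".
- Under Protocol 9.2, at six-month intervals, "subjects will undergo repeat upper and lower endoscopy".
- SAP 7.3 expects that "FAP event detection will cluster around scheduled study visits, at months 6, 12, 18, 24, 30, 36, 42 and 48".

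**The concern.** A missed-assessment rule normally deals with an event found after a long unobserved gap, when its true date is uncertain. This one has no such limit: two misses at any time trigger it, even if adequate endoscopies in between showed the subject event-free. It speaks of the missing assessment in the singular when there are at least two, so the censoring date is open. Nor is it clear whether an assessment is the upper endoscopy, the lower endoscopy, or the visit comprising both.

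Two analysts following the SAP could therefore put different events and censoring dates into the primary stratified log-rank test, and the choice could be made after the data are seen. Events are scarce: Protocol 3.2 reports "As of June 2017, there have been 53 FAP-related primary endpoint events", against a target of 90. Extension to 48 months gives up to eight scheduled endoscopy visits, so scattered misses have longer to accumulate.

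**Working it through.** **1. The rules applied to cases**

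- *Months 12 and 30 missed; examined at 18 and 24; event at 36.* Under the general event sentence this is an event at month 36. Under the missing-assessment rule it is censored at month 6 (first miss sets the date) or month 24 (second miss sets it). One SAP gives three codings.
- *Months 18 and 24 missed; event found at a close-out endoscopy.* This is an event if SAP 5.5.6 governs and is censored at month 12 if 5.5.3 governs.
- *Death after two scattered misses.* Death is part of the endpoint, and the rule does not exempt it.

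**2. Chance that one event is discarded**

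The documents give no missed-visit rate. Assume each six-monthly visit is missed independently with probability m. With n earlier visits that could have been missed, the chance of two or more misses is 1 − (1 − m)^n − n·m·(1 − m)^(n−1).

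Protocol 8.2.9 admits a subject to the extension only if all month 24 procedures were completed. For an event first seen after month 24, month 24 therefore cannot be one of the misses. So n = 3 for an event at month 24, 4 at month 36 (months 6, 12, 18, 30) and 6 at month 48.

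| m | event at 24 | event at 36 | event at 48 | two visits just before the event both missed, m² |
|---|---|---|---|---|
| 3% | 0.3% | 0.5% | 1.2% | 0.09% |
| 5% | 0.7% | 1.4% | 3.3% | 0.25% |
| 10% | 2.8% | 5.2% | 11.4% | 1.0% |

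The last column applies when both of those visits could be missed. It is zero where one of them is month 24, as for an event at month 36.

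**3. Expected events lost in the trial**

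Inputs from the documents: 171 subjects; accrual July 2014 to April 2016; treatment caps of 36, 42 or 48 months by randomization date; stop at 90 events or 30 April 2019; hazard ratio 0.4243; 53 events by June 2017. Assumptions: 57 per arm, uniform accrual, one stratum, exponential event times calibrated to about 53 detected events by June 2017, detection at the first attended six-monthly visit, dropout of zero or about 10% a year, and follow-up ending at a missed month 24.

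| Visits missed | Events lost, literal rule | Same, ignoring the month 24 condition (no dropout) |
|---|---|---|
| 3% | about 0.3 | about 0.5 |
| 5% | 0.7 to 0.9 | about 1.2 to 1.3 |
| 10% | 2.5 to 3.1 | about 4.6 |

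Expected totals are roughly 79 to 87 events. The lower losses go with dropout and the upper ones without. As shares: 0.3/79 to 0.3/87 is 0.3% to 0.4%; 0.7/79 to 0.9/87 is 0.9% to 1.0%; 2.5/79 to 3.1/87 is 3.2% to 3.6%. A rule limited to two consecutive misses just before the event would lose about 1.0 event at 10% missed (no dropout), against 3.1.

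**4. A rough guide to power**

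With d events in a comparison, power ≈ Φ(√(d/4)·|ln 0.42428| − 1.962). At d = 52 this is Φ(3.606 × 0.8574 − 1.962) = Φ(1.129) = 87.1%, matching the 0.8705 in SAP Table 5.1. Losing 1.0% of events (d = 51.5) gives 86.7%; losing 3.6% (d = 50.1) gives 85.8%. This counts events only and ignores the effect of moving censoring dates.

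**The case against.** SAP 5.5.3 can be read as a default followed by exceptions. The no-baseline rule has the same form, and nobody would call that a conflict. The close-out rule speaks of a single missed visit, so the sections can be read side by side: one miss, use close-out; two or more, censor. A reader might infer that the SAP flatly contradicts itself. The documents do not support that, because these readings are available. What stands is that none of them is stated, and none settles whether misses must be consecutive, which miss sets the date, or what happens to a death.

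The rule might also be meant only for event-free subjects. No event would then be lost, but event-free time confirmed by later endoscopies would be dropped: from the first miss or from the second, depending on which sets the date.

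A reader might infer a material loss of power or a real chance of a changed trial result. The documents do not support that either. They give no missed-visit rate, and three-monthly dispensing together with the cumulative-delay removal rule makes the low end more plausible, although dispensing by special arrangement is allowed. A model that ignores the month 24 condition overstates the loss: its figures are about half as large again as those that respect it.

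If upper and lower endoscopies were counted separately, one missed visit would already be two missing assessments. An event at month 24 would then be censored with probability 1 − 0.97³ = 8.7% at 3% missed, or 1 − 0.95³ = 14.3% at 5%. The text does not exclude this, but it is not the likeliest meaning and the loss estimates do not use it.

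**Conclusion.** The concern holds as a defect of specification, and it is minor. Followed literally, the rule discards documented primary events, deaths included, after scattered misses with adequate endoscopies in between, and the SAP does not say which of its rules prevails.

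The expected effect is well under 1% of events at 3% missed, about 1% at 5% and about 3% to 4% at 10%. On event counts alone, power per comparison falls by about 0.3 points at 5% (87.1% to 86.7% before rounding) and 1.2 points at 10%. These sizes rest on assumed, independent misses and a one-stratum model; misses related to treatment or disease could act differently by arm, which the documents do not allow one to judge. No bias or inflation of type I error has been shown. The reason to act is that the primary event set should be fixed before the data are seen.

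**What to change.** Amend the SAP before database lock:

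- State that a documented FAP-related event or death is not censored because of scattered earlier misses.
- Limit any missed-assessment censoring to two or more consecutive missed scheduled endoscopy visits immediately before the event, dated at the last adequate endoscopy before the first of those misses, and never apply it to death.
- Keep event-free subjects at risk to their last adequate endoscopy.
- Define assessment: upper, lower or both, including for subjects in whom only one procedure applies.
- State precedence relative to the close-out rule, and align Protocol 12.1.
- Name either counting all events or the consecutive-miss rule as primary, with the other as a sensitivity analysis. Either is defensible; what matters is to choose in advance.
- Record which rule any interim Z-score used. The interim was planned at 45 events and 53 had accrued by June 2017, so one may already have been computed.

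The cost is a few sentences, with no new data or visits. If all events are primary, an event found after a long gap carries a later and less precise date; the consecutive-miss sensitivity analysis covers that.

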### 3.2 Study Objectives

The primary study analysis will be performed using the intent-to-treat (ITT) population which is defined in Section 4.1. Statistical methods for the primary analysis are described in Sections 5.1 and 5.5.3.

The primary objective of this trial is to determine whether the combination of CPP-1X + sulindac is superior to either single-agent treatment individually in delaying time from the date of randomization to the date to the first occurrence of any FAP-related event.

Thus the primary objective contains two treatment comparisons:

1. CPP-1X placebo + sulindac active vs. CPP-1X active + sulindac active,  
and
2. CPP-1X active + sulindac placebo vs. CPP-1X active + sulindac active

These two treatment comparisons will be performed sequentially, as described below.

The combination of CPP-1X active + sulindac active is specified as the reference treatment group because it is common to both comparisons. In addition, because the purpose of the combination treatment is to delay the time from randomization to FAP-related disease progression compared to single-agent treatments, formulating the hypothesis tests in this manner will allow a positive rather than a negative Z-score for the test statistic to be interpreted as supportive of this purpose.

Each comparison will be performed at the 2-sided 0.05 level of statistical significance.

As explained in Section 3.2.1 below, the decision to seek regulatory approval based upon the results of the primary objective will be taken sequentially.

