### **3.2.1 Primary Analysis**

The primary analysis will be a time-to-event analysis using the stratified log-rank test. Graphical analyses (log-minus-log plots) will be used to check the assumption of constant hazard ratios with the COX model. See Section 7.3 below for further details of the calculation of the stratified log-rank statistic. The strata are the patient's sites of disease involvement at baseline, which is determined prior to randomization, and are: Rectal/pouch polyposis, Duodenal polyposis, and Pre-colectomy.

For the primary analysis, two stratified log-rank tests will be performed with treatment coded as a binary value (i.e., 0 or 1). Time to event curves will be displayed using the method of Kaplan and Meier[8]. Additional analyses involving the overall 3-treatment group comparison and use of additional study populations (see Section 4.) for the two pairwise treatment comparisons, will be performed as supplemental analyses. Refer to section 5.5.3 for further details.

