Prior to the primary analysis, balance will be assessed between the three arms in terms of key potential confounders measured at the baseline visit. If any of these variables is found significantly out of balance across the three groups using a 2 degree of freedom test of homogeneity at the 0.01 level of significance, it will be incorporated into a sensitivity analysis using a stratified Cox model including that term in addition to the treatment arm. The primary result for the trial will be the unadjusted stratified log-rank test. The covariate-adjusted score test (adjusted stratified log-rank test) will serve only as a secondary analysis to aid in the interpretation of the primary result.

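### The covariate-adjusted Cox sensitivity model is triggered by a baseline balance test at 0.01, so it will usually not exist when residual prognostic imbalance needs examining

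*SAP*

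**What the plan says.** SAP 5.5.3 plans a check of the three arms, before the primary analysis, on "key potential confounders measured at the baseline visit". These variables are not named. Balance is judged "using a 2 degree of freedom test of homogeneity at the 0.01 level of significance". A variable that fails is handled as follows: "it will be incorporated into a sensitivity analysis using a stratified Cox model including that term in addition to the treatment arm". Protocol 12.1 carries the same rule.

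The SAP is clear about rank. "The primary result for the trial will be the unadjusted stratified log-rank test", and the covariate-adjusted test "will serve only as a secondary analysis to aid in the interpretation of the primary result". SAP 7.3 confirms this for the primary model: "NB: The model includes the variables time, censor, and treatment, only". Disease site is handled separately as the stratification factor (SAP 3.2.1: "The strata are the patient's sites of disease involvement at baseline").

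SAP 5.5.3 also mentions stratified Cox models for secondary assessments but names no covariates for them. The balance-triggered model is therefore the only covariate-adjusted time-to-event analysis that is prespecified.

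**The concern.** In a randomised trial any baseline difference between arms is due to chance, so a significance test of that difference says nothing about whether the variable predicts the outcome. What moves a hazard ratio is the product of imbalance and prognostic strength, and the rule looks only at the first. A modest imbalance in a strong predictor is ignored, while a large imbalance in a weak one is admitted. The test also pools three arms, whereas each primary comparison involves two.

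The adjusted analysis has one purpose: helping the reader interpret the primary result. If its existence depends on a 1% test, it will seldom be available for that.

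Stratification does not remove every prognostic difference:

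- **Rectal/pouch stratum.** It combines patients with a retained rectum and patients with a pouch. For celecoxib-treated patients, Protocol Appendix E reports a later polypectomy in 90.9% after ileo-rectal anastomosis (median 18.69 months), against 3 of 24 (12.5%) after pouch surgery. Polypectomy is not the trial endpoint, but this suggests residual differences in risk.
- **Duodenal stratum.** Under Protocol 6.1 it combines current Spigelman stage 3 or 4 with patients treated down to stage 1 or 2. Stage progression is itself a primary event (Protocol 8.2.14), and a stage 4 patient cannot advance further in stage.

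**Working it through.** **Inputs from the documents.** 171 randomised (Protocol 3.2) at 1:1:1, so about 171/3 = 57 per arm. Balance test: 2 df, level 0.01. Design hazard ratio (HR) 0.4243, combination to single agent. 25 to 49 events needed and 50 to 55 expected per comparison (SAP 5.3). "Each comparison will be performed at the 2-sided 0.05 level of statistical significance".

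**Assumed, because the documents give no values.** A binary factor with 50% prevalence and prognostic hazard ratio g = 2 or 3.

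**The plan's own figure.** Events = 4(1.960 + 1.036)² / (ln HR)². For HR 0.4243: 35.91/0.735 = 48.9, so 49. For HR 0.30: 35.91/1.450 = 24.8, so 25. Both match SAP 5.3.

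**What the test misses.** χ² = n Σ(pᵢ − p̄)² / [p̄(1 − p̄)]. With 2 df, p = exp(−χ²/2), so the trigger is χ² > −2 ln 0.01 = 9.21.

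- Arms spread evenly, gap d between combination and one single-agent arm: χ² = 57(d²/2)/0.25 = 114d². Silent up to d = √(9.21/114) = 0.284.
- Combination differs by d from both single-agent arms: χ² = 57(2d²/3)/0.25 = 152d². Silent up to d = √(9.21/152) = 0.246.
- Example: 36, 28 and 20 of 57 gives χ² = 8.99, p = 0.011, so no adjustment.
- A 20-point gap against both arms: χ² = 6.08, p = 0.048, no adjustment. A 25-point gap: χ² = 9.50, p = 0.009, adjusted.

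At 30% prevalence the evenly spread limit is 26 points.

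**What a missed imbalance does.** Approximate shift = [1 + (g − 1)p₁]/[1 + (g − 1)p₂]. At the 28.4-point limit, p₁ = 0.642 and p₂ = 0.358:

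| g | shift | a true HR of 0.424 appears as |
|---|---|---|
| 2 | 1.642/1.358 = 1.21 | 0.513 or 0.351 |
| 3 | 2.284/1.716 = 1.33 | 0.565 or 0.319 |

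The two values depend on the direction of the imbalance.

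**How often.** Simulated randomisations, 57 per arm, one such factor:

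| g | HR shift of 10% or more in at least one comparison | rule fires in those cases |
|---|---|---|
| 2 | 22% | 4.5% |
| 3 | 49% | 2.0% |

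Over all randomisations the rule fires about 1% of the time per variable. For k independent variables the model is non-empty with probability 1 − 0.99ᵏ: 3%, 5% and 8% for k = 3, 5 and 8.

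**What always adjusting recovers.** Cox simulation at one fixed split (36/57 combination, 21/57 single agent, 29/57 third arm; χ² = 7.91, p = 0.019, not triggered), 1,000 replicates, 24 months, no dropout, no strata. With no treatment effect the unadjusted HR averages 1.20 (g = 2) or 1.33 (g = 3), close to the formula's 1.19 and 1.30; adjusted it is 1.00. At a true HR of 0.424 the unadjusted estimate is 0.52 or 0.60 and the adjusted one 0.42. Part of that last gap is the attenuation that comes from omitting any strong predictor, not the imbalance alone.

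**The case against.** The strongest reply is that no decision depends on this rule. The primary test is unadjusted whatever the balance check shows, and success, alpha and gatekeeping do not use the adjusted model. This stands. A reader might infer that the primary result is biased or its type I error inflated. The documents do not support that: over repeated randomisations the stratified log-rank test remains valid, and the distortions above are conditional on a particular imbalance.

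The main prognostic factor is already controlled. SAP Table 3.1 projects two-year event-free rates from 10% (pre-colectomy) to 40-60% (rectum/pouch), and this factor is stratified in both randomisation and analysis. This also stands, and limits the point to factors within strata.

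The size rests on assumed inputs, and large gaps are uncommon. A gap of 20 points or more between combination and the pooled single-agent arms has standard error √[0.25(1/57 + 1/114)] = 0.081, so z = 2.47 and a probability of about 1.4% per factor. Such a gap would also show as significant in the descriptive comparison at 0.05 in SAP 5.5.1, though it would not be adjusted for. A 10% shift is small against sampling error: at 49 events the standard error of log HR is about 2/√49 = 0.29, and ln 1.1 = 0.095 is a third of that. These are fair limits on importance. They do not make the trigger a sound selection rule.

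A reader might also infer that the model will fill with irrelevant variables picked by chance. The SAP restricts the check to key confounders, which implies some prior selection. Reaching an 18% chance of any false trigger needs 20 variables, for which the documents give no basis. The likelier outcome is an empty model.

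**Conclusion.** The point holds as a cheap improvement to a secondary analysis. The balance test at 0.01 selects on the wrong property and, at this sample size, passes gaps of about 25 to 28 points in a factor with 50% prevalence. The undetected gap depends only on arm size and prevalence. Its effect on the hazard ratio depends on the assumed prognostic strength: with g = 2 to 3, a shift of 10% or more arises in roughly a fifth to a half of randomisations, and the rule responds in about one in twenty to one in fifty of those. The adjusted analysis will therefore usually be absent when it would help interpretation.

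Moving the threshold would not cure this, because any balance test still ignores prognostic strength. The conclusion does not extend to the primary test, its error rate or the control of disease site.

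**What to change.** In SAP 5.5.3 and Protocol 12.1, replace the balance trigger with a short list of baseline covariates fixed before unblinding. Enter them in the stratified Cox sensitivity model for each of the two comparisons, whatever the observed balance. Report the adjusted hazard ratio and interval beside the primary result, and keep the unadjusted stratified log-rank test as primary.

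Candidates already collected:

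- Post-snare baseline Spigelman stage (Protocol 9.1), coded in few levels, with a not-applicable level for patients without a duodenum.
- Rectal/pouch polyp-count category (Protocol 9.1) or surgical status (SAP Table 3.3), with a not-applicable level for an intact colon or ileostomy where needed.
- Age.

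The documents do not establish these as the definitive set, so the choice and coding should be settled on clinical grounds without sight of treatment codes. The not-applicable levels matter, because otherwise the model would drop patients who lack the organ.

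The cost is matching wording in two documents and about three to five degrees of freedom against the 50 to 55 events expected per comparison. Protocol 3.2 reports 53 events across all arms by June 2017 and doubts that 90 will be reached, so the final count may be lower and the coding should stay sparse.
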